1.2. Study Design

This is a randomized, double-blind, placebo-controlled, parallel-group, multicenter study to evaluate the efficacy and safety of guselkumab SC induction therapy in adult participants with moderately to severely active UC defined as a modified Mayo score of 5 to 9, inclusive, Mayo rectal bleeding subscore ≥ 1 and a Mayo endoscopy subscore ≥ 2 . Participants must have demonstrated an inadequate response to or intolerance of conventional (i.e., 6-mercaptopurine (6-MP), azathioprine (AZA), or corticosteroids) or advanced therapy (ADT; i.e., tumor necrosis factor (TNF) α antagonists, vedolizumab, ozanimod, or approved Janus kinase (JAK) inhibitors). An overview over the study design is given in Figure 1.

A target of 399 participants will be enrolled in this study with 133 participants planned per intervention group. Participants who had an inadequate response to or intolerance of advanced therapy (ADT-IR) will comprise a minimum of approximately 40% and a maximum of approximately 50% of the population. Consented participants will be screened for study eligibility within 8 weeks of the Week 0 visit. Eligible participants will be randomized in a 1:1:1 ratio to the following intervention groups:

- Guselkumab CCI at Weeks 0, 4, and 8 followed by guselkumab 200 mg SC q4w through Week 24
- Guselkumab CCl at Weeks 0, 4, and 8 followed by guselkumab 100 mg SC q8w through Week 24
- Placebo SC q4w from Week 0 through Week 24

Participants will be allocated to an intervention group using permuted block randomization stratified by ADT-IR status (Yes/No) and Mayo endoscopy subscore at baseline (moderate [2] or severe [3]).

At weeks 12 and 16, all participants will be evaluated according to predefined rescue criteria as given below. All participants in the placebo group who meet rescue criteria at Week 16 will receive rescue treatment, i.e., guselkumab at Weeks 16, 20, and 24 followed by guselkumab 100 mg SC q8w. Participants randomized to guselkumab who meet rescue criteria at Week 16 will continue their assigned treatment regimen and receive blinded sham rescue with matching placebo SC injections at Weeks 16, 20, and 24.

Rescue criteria are defined as:

• No improvement (i.e., no decrease) in Mayo endoscopy subscore at Week 12, when compared with baseline

AND

• A <2 point improvement (i.e., <2 point decrease) in partial Mayo score at Weeks 12 and 16, when compared with baseline

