3. SAMPLE SIZE DETERMINATION

Sample size was determined by the power to detect significant differences in the primary endpoint of clinical remission at Week 12, and by the objective of maintaining at least 85% power across secondary endpoints at Week 12 between the combined guselkumab SC induction groups and the placebo SC group as well as for symptomatic remission at Week 24 between each guselkumab group and the placebo group, using 2-sided χ^2 tests with significance level 0.05. Combination of guselkumab SC induction groups for the primary endpoint and other Week 12 endpoints is warranted by the fact their treatment is identical through the induction period, and only differs after assessment of the primary endpoint at Week 12.

With assumed clinical remission rates of 8% for placebo and 22% for the combined guselkumab groups (based on data from Phase 2b guselkumab UC IV induction study [CNTO1959UCO3001] and Phase 3 ustekinumab UC program [CNTO1275UCO3001]), a total of 399 participants (randomized 1:1:1 for guselkumab CC q4w [Weeks 0, 4, and 8] followed by guselkumab 200 mg SC q4w: guselkumab q4w [Weeks 0, 4, and 8] followed by guselkumab 100

mg SC q8w: Placebo, yielding a 2:1 guselkumab:placebo randomization ratio for Week 12 comparisons) will ensure >95% power for the primary endpoint. This sample size also protects against a slightly lower remission rate of 20% for the combined guselkumab groups or a slightly higher remission rate of 9.5% in the placebo group (as observed in CNTO1959UCO3001), yielding a power of 90% in both cases.

Individual power values (ie, without consideration of an adjustment for multiplicity) achieved for secondary endpoints at Week 12 with a total of 399 participants (2:1 guselkumab:placebo) are described in Table 2.

Table 2: Power for Secondary Endpoints at Week 12

Endpoints	Proportion achieving endpoint in Placebo group	Proportion achieving endpoint in combined Guselkumab group	Power
Symptomatic remission	20%	45%	>99%
Endoscopic improvement	13%	28%	94%
Clinical response	30%	60%	>99%
Histologic-endoscopic mucosal improvement	8%	19%	85%
Assumed rates were based on data from the Phase 2b guselkumab UC IV induction study and the Phase 3 ustekinumab UC program			

For the secondary endpoints at Week 24, power is determined by the pairwise comparison of individual guselkumab groups to placebo (see Table 3).

Table 3: Power for Secondary Endpoints at Week 24 with a Total of 399 Participants (133 per Treatment Group)

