- Sustained clinical remission: Clinical remission at Week 12 and Week 24 (Week 24 DBL) and at Week 12, Week 24 and Week 48 (Week 48 DBL)
- Maintenance of clinical remission at Week 24 and at Week 48 among participants achieving clinical remission at Week 12
- Maintenance of clinical remission through Week 48 (at both Week 24 and Week 48) among participants achieving clinical remission at Week 12
- Sustained clinical response: Clinical response at Week 12 and Week 24 (Week 24 DBL), Week 12, Week 24 and Week 48 (Week 48 DBL)
- Symptomatic remission over time among participants achieving symptomatic remission at Week 12 (Week 48 DBL only)
- Durable symptomatic remission through Week 48: Defined as achieving symptomatic remission for >80% of all visits between Week 0 (excluding) and Week 48 (including)

The changes from baseline over time will be evaluated for full Mayo score, modified Mayo score, partial Mayo score, and Mayo stool frequency and rectal bleeding and subscores. The full Mayo score and the modified Mayo scores require an endoscopy and will therefore only be evaluated at Week 12, Week 24 and Week 48. The partial Mayo score will be evaluated at all visits.

The following evaluations for completeness/missingness of the Mayo score will be done at Week 12, Week 24 and Week 48:

- Summary of completeness of modified Mayo score and the full Mayo score
- Number of participants who experienced intercurrent events prior to Week 12, prior to Week 24 and prior to Week 48
- Summary of Mayo subscores through Week 12, through Week 24, and through Week 48
- Summary of missing modified Mayo score and the full Mayo score components after accounting for ICE strategies and by intercurrent event occurrence

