- Deep histologic-endoscopic mucosal remission: Defined as combination of histologic remission (defined as absence of neutrophils from the mucosa [both lamina propria and epithelium], no crypt destruction, and no erosions, ulcerations or granulation tissue according to the Geboes grading system) and endoscopic normalization (endoscopy subscore of 0), as defined above
- Combination of clinical remission and histologic remission (i.e., symptomatic remission, endoscopic improvement and histologic remission) at Week 48
- Combination of histologic-endoscopic mucosal improvement (alternative definition 1, as defined above) and symptomatic remission and fecal calprotectin normalization (defined as fecal calprotectin concentration ≤ 250 mg/kg) at Week 48
- Combination of deep histologic-endoscopic mucosal remission (as defined above) and symptomatic remission and fecal calprotectin normalization (defined as fecal calprotectin concentration ≤ 250 mg/kg) at Week 48

- Sustained endoscopic improvement: Endoscopic improvement at Week 12, Week 24 and Week 48
- Maintenance of endoscopic improvement at Week 48 among participants achieving endoscopic improvement at Week 12
- Maintenance of endoscopic improvement through Week 48 (at both Week 24 and Week 48) among participants achieving endoscopic improvement at Week 12

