5.5.4. Analysis Methods

Unless otherwise specified, the exploratory endpoints listed and defined in Sections 5.5.1 to 5.5.3 will be analyzed based on the FAS according to the randomized intervention group, regardless of the intervention actually received.

No confirmatory tests will be performed on exploratory endpoints, regardless of the significance for primary and secondary endpoints. Nominal p-values will be presented without adjustments for multiple comparisons.

Descriptive statistics (mean, median, SD, IQ range, minimum, and maximum) will be used to summarize continuous variables. Counts and percentages will be used to summarize categorical variables. Graphical data displays (e.g., line plots) may also be used to summarize the data.

Binary endpoints

The main estimand approach and the estimator used for the secondary endpoints (Section 5.4.1.2) will be used to summarize and compare binary endpoints. Intercurrent events will be handled as specified in Table 6.

The handling of ICEs specified in Section 5.4.1.2 will be applied to each of the above binary endpoints. Participants with ICEs in categories 1-4 and 6 will be considered not to have achieved the binary endpoint, while observed values will be used for participants experiencing an ICE in category 5.

Participants with any missing data for an endpoint after application of ICE handling rules will be imputed as not having achieved the associated binary endpoint. Binary endpoints will be summarized with the number and percentage of participants who achieve the endpoint by intervention group. To compare the proportion of participants achieving the endpoints, MH tests stratified by the ADT-IR status (Yes/No), and Mayo endoscopy subscore at baseline (moderate [2] or severe [3]) will be provided. In case of rare events, Fisher's exact test will be used for intervention comparisons.

Continuous endpoints

For continuous endpoints, handling rules for ICEs as defined in Table 6:

- Composite strategy (categories 1-4 and 6): Baseline values will be assigned from the point of ICE onward
- Treatment policy strategy (category 5): Observed values will be used, if available

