5.5.4.1. Subgroup Analyses

Subgroup analyses for subgroups defined by the stratification variables (ADT-IR yes/no, baseline endoscopic subscore moderate [2]/severe [3]) will be performed using the FAS for the following exploratory endpoints (all as defined in Section 5.5.1.2):

- Histologic improvement
- Histologic remission
- Combination of histologic remission and endoscopic improvement

The following analysis approach will be applied:

- The consistency of intervention effect will be evaluated, using the main estimand and handling missing data by the rules specified in Section 5.4.2.1.
- The adjusted treatment difference of the combined guselkumab SC group vs. the placebo SC group and the associated p-values and 95% confidence intervals will be provided. The treatment differences, p-values and confidence intervals will be obtained from a MH test stratified by the remaining stratification factor.

In addition, descriptive analyses will be performed for the rescue analysis set for the following endpoints:

- Clinical remission (primary definition as given in Table 10 only) at Week 48
- Symptomatic remission over time
- Change from baseline in partial Mayo score over time
- 8-week corticosteroid-free clinical remission at Week 48: Defined as being in clinical remission at Week 48 and not having received corticosteroids between Week 40 and Week 48
- Change from baseline in CRP concentration [mg/L] over time
- Change from baseline in fecal calprotectin concentration [mg/kg] over time

Descriptive analyses will be performed for the Week 12 Clinical Responder Analysis Set for the following endpoints:

- Clinical remission at Week 24 and at Week 48
- Symptomatic remission over time
- Deep symptomatic remission at Week 24 and at Week 48
- Mayo stool frequency subscore of 0 or 1 over time
- Mayo rectal bleeding subscore of 0 over time
- Clinical response at Week 24 and at Week 48
- Clinical response through Week 48 (at both Week 24 and Week 48)
- Endoscopic normalization at Week 24 and at Week 48
- Endoscopic improvement at Week 24 and at Week 48
- Change from baseline in CRP concentration [mg/L] over time
- Change from baseline in fecal calprotectin concentration [mg/kg] over time
- Deep symptomatic remission (Mayo stool frequency subscore of 0 and Mayo at rectal bleeding subscore of 0) over time

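### Exploratory endpoints restricted to Week 12 remitters or improvers get nominal p-values against placebo by default, although the subsets are formed by a post-randomisation outcome

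*SAP*

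**What the plan says.** SAP 5.5.1.1 lists two endpoints among Week 12 clinical remitters: "Maintenance of clinical remission at Week 24 and at Week 48 among participants achieving clinical remission at Week 12" and "Maintenance of clinical remission through Week 48 (at both Week 24 and Week 48) among participants achieving clinical remission at Week 12". It also lists symptomatic remission over time among those in symptomatic remission at Week 12. SAP 5.5.1.2 adds "Maintenance of endoscopic improvement at Week 48 among participants achieving endoscopic improvement at Week 12" and a version requiring improvement at both Week 24 and Week 48.

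Neither section states an analysis method for these endpoints. SAP 5.5.4 covers everything defined in 5.5.1 to 5.5.3 unless specified otherwise. Its rule for binary endpoints reads "To compare the proportion of participants achieving the endpoints, MH tests stratified by the ADT-IR status (Yes/No" and continues with baseline endoscopy subscore as the second factor, giving four strata. Fisher's exact test replaces this for rare events, with no threshold given. P-values are nominal and unadjusted, and no confirmatory testing is done.

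For another set defined by a Week 12 outcome, SAP 5.5.4.1 takes a different route: "Descriptive analyses will be performed for the Week 12 Clinical Responder Analysis Set".

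**The concern.** Being a Week 12 remitter is the primary endpoint itself. If guselkumab works as planned, the guselkumab subset contains participants who would also have remitted on placebo plus others who remitted only because of the drug. The placebo subset contains few or none of the second kind. The two subsets can therefore differ in prognosis before any question of maintenance arises, and a p-value between them does not test a randomised treatment effect. The same holds for subsets defined by Week 12 endoscopic improvement or symptomatic remission.

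What is at stake is interpretation. A p-value attached to a maintenance endpoint invites reading as evidence on maintenance, and nothing in the SAP tells the reader that the comparison is non-randomised.

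**Working it through.** **Inputs from the documents.** Group size: "A target of 399 participants will be enrolled in this study with 133 participants planned per intervention group" (SAP 1.2). Week 12 remission: "With assumed clinical remission rates of 8% for placebo and 22% for the combined guselkumab groups" (SAP 3). Alternative placebo rate: "higher remission rate of 9.5% in the placebo group (as observed in CNTO1959UCO3001" (SAP 3). From SAP Table 2, placebo against combined guselkumab: endoscopic improvement 13% and 28%; symptomatic remission 20% and 45%.

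**The plan's own figure.** A two-sided chi-square test at 0.05 with 133 placebo and 266 guselkumab participants, 8% against 22%, gives 96.1% power. The SAP states more than 95%, so the planning inputs reproduce.

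**Expected subset sizes** (133 x rate; 2.5th to 97.5th binomial percentiles in brackets):

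| Week 12 condition | Placebo | Each guselkumab arm |
|---|---|---|
| Clinical remission | 133 x 0.08 = 10.6 (5 to 17) | 133 x 0.22 = 29.3 (20 to 39) |
| Clinical remission, 9.5% placebo rate | 133 x 0.095 = 12.6 (6 to 20) | as above |
| Endoscopic improvement | 133 x 0.13 = 17.3 (10 to 25) | 133 x 0.28 = 37.2 (27 to 48) |
| Symptomatic remission | 133 x 0.20 = 26.6 (18 to 36) | 133 x 0.45 = 59.9 (49 to 71) |

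**Selection effect for clinical remission.** Assume that everyone who would remit on placebo (8%) would also remit on guselkumab, that a further 14% (22% - 8%) remit only on drug, and that drug has no effect on maintenance after Week 12. Let a be the maintenance rate in either-arm remitters and b the rate in drug-only remitters. Neither rate is in the documents.

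- Placebo subset rate = a.
- Guselkumab subset rate = (0.08a + 0.14b) / 0.22.

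| a | b | Placebo | Guselkumab | Apparent difference |
|---|---|---|---|---|
| 70% | 45% | 70% | (0.056 + 0.063)/0.22 = 54.1% | -15.9 points |
| 60% | 60% | 60% | (0.048 + 0.084)/0.22 = 60.0% | 0 |
| 50% | 70% | 50% | (0.040 + 0.098)/0.22 = 62.7% | +12.7 points |

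The subset comparison changes sign with the assumed rates although drug does nothing after Week 12 in any row.

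**The FAS counterpart.** Remission at both Week 12 and the later visit, counted over all participants, is 0.08 x 0.70 = 5.6% against 0.22 x 0.541 = 11.9% in the first row, and 4.0% against 13.8% in the third. That comparison keeps the randomised groups.

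**Precision at 11 against 29.** With assumed rates of 40% and 60%, the 95% half-width for the difference is 1.96 x sqrt(0.4 x 0.6/11 + 0.6 x 0.4/29) = 0.34, or 34 points. Power for that difference is 20% by chi-square and 16% by Fisher's test.

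**The case against.** The strongest reply is that little rests on these endpoints. SAP 2 calls all Week 48 endpoints exploratory, SAP 5.5.4 rules out confirmatory testing, and the randomised alternatives are already listed: sustained clinical remission, sustained clinical response and durable symptomatic remission in 5.5.1.1, and sustained endoscopic improvement in 5.5.1.2. The p-values are also inferred from a default rule, not announced for these endpoints by name. All of this stands and limits the severity. It does not change what the p-value would mean: the exploratory label and the word nominal concern multiplicity and status, and Fisher's test concerns small counts. None addresses selection.

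Sparse strata are not a strong argument by themselves, because MH weighting is built to combine them.

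Three stronger readings are tempting, and the documents do not support them.

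- A reader might infer that the SAP contradicts itself by handling the Week 12 Clinical Responder Analysis Set descriptively. The SAP version history gives internal comparison with another study's maintenance data as a reason for adding that set, so its handling is not a judgement that such p-values are invalid. It is a useful precedent, no more.
- A reader might infer that placebo remitters are spontaneous remitters. Protocol 6.8.1 allows stable oral 5-ASA, corticosteroids and immunomodulators, so background therapy may contribute.
- A reader might take the -16 points as the size of the bias. It is one assumed scenario among several, and the sign can reverse.

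**Conclusion.** The point holds as a modest, inexpensive improvement to the SAP. Under the default rule in 5.5.4, binary endpoints conditioned on a Week 12 outcome receive nominal p-values against placebo that are not protected by randomisation. The direction of bias is unknown: about -16 to +13 points for clinical remission across the scenarios shown. These rest on assumed maintenance rates, no placebo-only remitters and no drug effect after Week 12. They show what is possible and do not estimate the bias.

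The placebo counts are planning expectations; the SAP states no subset sizes. The figure of about 11 (about 13 at the 9.5% rate) belongs to clinical remission only and should not be carried over to endoscopic improvement (about 17) or symptomatic remission (about 27). No primary or secondary result, and no part of the multiplicity procedure, is affected.

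**What to change.** Add one sentence to SAP 5.5.4: endpoints restricted to participants with a given Week 12 outcome are summarised descriptively by arm (n/N, percentage, within-arm confidence interval), with no between-arm p-value, in line with the Week 12 Clinical Responder Analysis Set in 5.5.4.1. State there that comparisons with placebo rest on the FAS sustained and durable endpoints already in 5.5.1.1 and 5.5.1.2.

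The cost is a few nominal p-values. The FAS endpoints combine reaching an outcome with keeping it, so they do not isolate maintenance, but they do compare randomised groups. Sample size, data collection and confirmatory testing are unchanged.

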5.5.1.2. Histology and Endoscopy Based Endpoints

The following endpoints will be analyzed at Week 12, Week 24 (endoscopy based endpoints only) and Week 48:

- Endoscopic normalization: Defined as a Mayo endoscopy subscore of 0.
- Endoscopic improvement as defined in Section 5.4.1.1

- Histologic improvement: Defined as neutrophil infiltration in <5% of crypts, no crypt destruction, and no erosions, ulcerations or granulation tissue according to the Geboes grading system
- Histologic improvement as defined above in participants not meeting histologic improvement criteria at baseline
- Histologic remission: Defined as absence of neutrophils from the mucosa (both lamina propria and epithelium), no crypt destruction, and no erosions, ulcerations or granulation tissue according to the Geboes grading system
- Histologic-endoscopic mucosal improvement as defined in Section 5.4.1.1
- Summary of change from baseline in Robarts Histopathology Index⁷⁾ (see Appendix 13)
- Summary of change from baseline in Geboes total score, where the continuous histology score is derived as the sum of all Geboes Grades and may take on values from 0 to 22
- Summary of change from baseline in Geboes high activity subscore, where the continuous histology score is derived as the sum of Geboes Grades 3, 4, and 5 that define histologic healing and may take on values from 0 to 10
- Summary of change from baseline in Geboes low activity subscore, where the continuous histology score is derived as the sum of Geboes Grades 0, 1, 2A and 2B and may take on values from 0 to 12
- Summary of change from baseline in Nancy Histological Index
- Histologic remission based on the Nancy Histological Index: Defined as Nancy Histological Index⁵⁾ score ≤1 (see Appendix 12)
- Histologic-endoscopic mucosal improvement (alternative definition 1): Defined as a combination of histologic remission (defined as absence of neutrophils from the mucosa [both lamina propria and epithelium], no crypt destruction, and no erosions, ulcerations or granulation tissue according to the Geboes grading system) and endoscopic improvement (endoscopy subscore of 0 or 1 with no friability), as defined above
- Deep histologic-endoscopic mucosal remission: Defined as combination of histologic remission (defined as absence of neutrophils from the mucosa [both lamina propria and epithelium], no crypt destruction, and no erosions, ulcerations or granulation tissue according to the Geboes grading system) and endoscopic normalization (endoscopy subscore of 0), as defined above
- Combination of clinical remission and histologic remission (i.e., symptomatic remission, endoscopic improvement and histologic remission) at Week 48
- Combination of histologic-endoscopic mucosal improvement (alternative definition 1, as defined above) and symptomatic remission and fecal calprotectin normalization (defined as fecal calprotectin concentration ≤ 250 mg/kg) at Week 48
- Combination of deep histologic-endoscopic mucosal remission (as defined above) and symptomatic remission and fecal calprotectin normalization (defined as fecal calprotectin concentration ≤ 250 mg/kg) at Week 48

- Sustained endoscopic improvement: Endoscopic improvement at Week 12, Week 24 and Week 48
- Maintenance of endoscopic improvement at Week 48 among participants achieving endoscopic improvement at Week 12
- Maintenance of endoscopic improvement through Week 48 (at both Week 24 and Week 48) among participants achieving endoscopic improvement at Week 12

